8.5.5 Adjustment of Confidence Intervals and p-values

An interim analysis will be performed after 50% of the participants needed has been accrued/included. The analysis will focus on the primary outcome and on safety. The non-inferiority design of the study means that a clear disadvantage of the PCT-guided treatment arm or in other words a clear benefit of the usual care arm will lead to discontinuation of the trial. The p-value at the interim analysis will be 0.0054 according to the O'Brien-Fleming method, and the p-value at final analysis will be 0.0492 [14]. The safety data consists of observed adverse events and SAE. The safety data consists of observed adverse events and SAE. The change of the p-value at final analysis will lead to an increase of 2 patients per treatment arm. The number of patients per treatment arm will be 315. Using a 10% drop-out rate this will lead to a total number of patients of 693.

8.5.6 Practical Measures to Minimize Bias

An interim analysis will be performed at 50% of patient accrual, analysing the primary outcome and safety data. The safety data consists of observed adverse events and SAE. The interim analysis will be performed by a Data Safety Monitoring Board (DSMB) comprised of dr. [name] (pulmonologist Franciscus Gasthuis, Rotterdam) dr. [name] (medical microbiologist

Erasmus Medical Center, Rotterdam) and prof. dr. ir. [name] (professor of clinical epidemiology, Erasmus Medical Center). These three individuals will be the only persons with knowledge of the data at the interim analysis. The advice of the DSMB will only be sent to the principal investigator. Should the principal investigator decide not to fully implement the advice of the DSMB, the principal investigator will send the advice to the reviewing Ethical Committee (in Dutch: METC), including a note to substantiate why (part of) the advice of the DSMB will not be followed.

8.6 Multiple Testing

Op dit moment niet van toepassing, mogelijk nog wanneer primair eindpunt zou veranderen.

9 Summary of Study Data

Table 1. Baseline characteristics

The baseline characteristics are given in the table below.

	Usual care (n = 308)	PCT-guided treatment (n = 308)
Age in years – mean±SD		
Male gender – no. (%)		
BMI – mean±SD		
Smoking status: - current – no. (%) - past – no. (%) - pack years (mean, range)		
FEV1 % predicted - mean±SD		
GOLD classification: - I – no. (%) - II – no. (%) - III – no. (%) - IV – no. (%)		
Exacerbation type: - type I – no. (%) - type II – no. (%) - type III – no. (%)		
Median duration of symptoms in days - mean±SD		
CRP in mg/L – median [IQR]		
WBC 10 ⁹ /L – mean±SD		
CAT score – median [IQR]		
EXACT- RS score – median [IQR]		

Primary outcome

The primary outcome will be treatment failure within 30 days. A non-inferiority margin of 5% will be used to assess non-inferiority. Treatment failure is defined as disease-related mortality, endotracheal intubation, vasopressors, renal failure, lung abscess/empyema, development of pneumonia and hospital readmission within 30 days.

- Binary outcome parameter: yes or no. Description: number and percentage.
- To account for the multicenter effect a logistic mixed effects model will be estimated with

centers as random effect and treatment group as fixed effect to analyze the primary outcome. The risk of primary endpoint in the PCT guided treatment arm versus the usual care treatment arm will be reported with an odds ratio from the logistic model, with a 95% confidence interval. Based on this CI we will determine non-inferiority of the treatment.

Secondary outcome parameters

Skewed data will be analyzed using non-parametric tests. Paired measurements will be analyzed using paired tests.

The quality of life endpoints, using the COPD Assessment Test (CAT) and the EXACT-respiratory symptoms questionnaire, consist of multiple (three) measurements per subject. These measurements are all performed on the same time point (baseline, day 10 and day 30). These endpoints will be scored using the mean score and standard deviation when normally distributed and a median with the inter quartile range when the data have a skewed distribution. These data will be analyzed with a mixed effects model with random effects for center and patient to account for the extra hierarchical level in the data. The residuals will be evaluated for normality to test the assumptions of the models. In case of violations, transformations will be conducted on the dependent variable.

The unpaired continuous variables will be reported using the mean score and the standard deviation (normal distribution) or the median with the inter quartile range (skewed distribution). These variables will be analyzed using an mixed effects model.

The frequency and percentage will be reported for the categorical (mostly dichotomous) variables. Analysis of these variables will be performed using a logistic mixed-effects model.

- The analysis populations upon which the tables and figures will be based will be the per-protocol analysis population.

Table 2. Primary endpoint and secondary endpoints

	PCT-guided treatment (n = 315)	Usual care (n = 315)		p-value
Primary endpoint:				
Overall treatment failure:	n (%)	n (%)	OR (95% CI)	
- Disease-related mortality	n (%)	n (%)		
- Endotracheal intubation	n (%)	n (%)		
- Vasopressors	n (%)	n (%)		
- Renal failure	n (%)	n (%)		
- Lung abscess/empyema	n (%)	n (%)		
- Pneumonia development	n (%)	n (%)		
- Hospital readmission	n (%)	n (%)		
Secondary endpoints				
Incomplete resolution of the clinical signs and symptoms at day 30 after (scored using the modified Anthonisen criteria)	n (%)	n (%)	OR (95% CI)	

Change in QoL using the CAT: after 10 days after 30 days	mean (SD)or median [IQR]	mean (SD)or median [IQR]		
Start of antibiotic therapy after an initial opposite decision (after 48 hours)	n (%)	n (%)	OR (95% CI)	
Side effects (gastro-intestinal complaints, allergic reactions)	n (%)	n (%)	OR (95% CI)	
Cumulative antibiotic consumption	mean/median days (SD) or [IQR]	mean/median days (SD) or [IQR]		
Cumulative prednisolone consumption	mean/median days (SD) or [IQR]	mean/median days (SD) or [IQR]		
Length of hospitalization	mean/median days (SD) or [IQR]	mean/median days (SD) or [IQR]		
Time to complete resolution of symptoms (modified Anthonisen criteria)	mean/median days (SD) or [IQR]	mean/median days (SD) or [IQR]		
Re-exacerbation within 30 days	n (%)	n (%)	OR (95% CI)	
EXACT – Respiratory symptoms scale, change: after 10 days after 30 days	mean (SD)or median [IQR]	mean (SD)or median [IQR]		
Non-Invasive ventilation (>72h)	n (%)	n (%)	OR (95% CI)	

Only deviations from the general overview will be noted in the subsequent sub-sections within section 9.

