## 2. OBJECTIVES

We hypothesize that at hospitalization for a severe acute exacerbation for COPD, biomarker-guided treatment based on procalcitonin level to guide antibiotic administration is non-

---

inferior to usual care consisting of prednisolone and or antibiotics, which is based on a clinical decision, in terms of treatment failure at day 30.

The secondary objectives are to establish that a biomarker-guided decision algorithm results in an improvement in quality of life, a decrease in consumption of antibiotics, and a reduction of important side effects.

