#### 8.1.2 Secondary study parameters/endpoints

The secondary objectives of this study are to assess the following secondary endpoints:-

The key secondary objective is:

- Treatment failure defined as an incomplete resolution of the clinical signs and symptoms associated with the AECOPD at day 30 after inclusion of the study (i.e not reaching the baseline condition prior to the AECOPD) scored using the modified Anthonisen criteria.

The other secondary objectives are:

- Change in Quality of Life on day 1, 10, and after 30 days using the COPD Assessment Test (CAT)
- Decision to start antibiotic therapy after an initial opposite decision (after 48 hours)
- Side effects (gastro-intestinal complaints, allergic reactions)
- Cumulative antibiotic consumption
- Cumulative prednisolone consumption
- Length of hospitalization
- Time to complete resolution of symptoms according to daily symptom diaries evaluating the modified Anthonisen criteria
- Re-exacerbation within 30 days
- PROM symptom score: EXACT – Respiratory symptoms scale (at admission, at day 10 and at day 30 after admission)
- Non-Invasive ventilation after 72 hours of admission

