### **Statistical and analytical plans**

#### **Primary analysis**

The primary endpoint is defined as 30-day treatment failure. The per protocol (PP) population is the main analysis population. An analysis will be performed for the randomly

---

allocated antibiotic strategy (i.e. usual care versus antibiotics in patients with PCT >0.25 µg/L). The difference and corresponding 95% confidence interval (two-sided) in the incidence of the primary endpoint between the randomly allocated strategies (biomarker-guided drug use minus drug-in-all) will be determined. Non-inferiority will be concluded if the upper limit of the 95% confidence interval does not exceed the prespecified non-inferiority margin of 5%.

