In international literature there is scarce information about the percentages of treatment failure in patients admitted with an AECOPD receiving usual care. Therefore, we have performed a further search on PCT studies with a primary outcome of 30-day treatment failure. In the study by Schuetz et al. [6], who studied patients with lower respiratory tract infection, 30-day treatment failure was observed in 15.5% of the patients randomised to biomarker-based treatment, as compared to 18.9% in those randomised to usual care. This implies a relative risk of 0.82 in favour of the biomarker-based strategy. The study by Schuetz et al. was designed as a non-inferiority study, using a non-inferiority boundary of 7.5%. In view of these data we decided to design our study as a non-inferior study, whereas we choose a non-inferiority boundary of 5.0%. We based the primary outcome on the study of Huang et al. [13]. The incidence of the primary outcome was 20.4%. Using the relative risk of 0.82 in favour of the PCT-guided treatment group we expect the incidence of the primary outcome to be 16.7% in the PCT-guided treatment group. Then a total sample size of 626 is required (313 per treatment arm) to demonstrate non-inferiority with a power of 80%, and applying a one-sided alpha error of 0.025. We aim to enroll a total of 690 patients, accounting for a 10% drop-out rate.

8 General Analysis Considerations

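### SAP 8.6 gives the three secondary objectives no testing order, and the per-protocol set biases the antibiotic-use comparison towards a reduction

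*SAP*

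**What the plan says.** SAP 8.6 consists of one Dutch sentence: "Op dit moment niet van toepassing, mogelijk nog wanneer primair eindpunt zou veranderen". It sets no order, no adjustment and no significance level for secondary endpoints.

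Protocol 2 states: "The secondary objectives are to establish that a biomarker-guided decision algorithm results in an improvement in quality of life". The sentence goes on to lower antibiotic consumption and fewer important side effects, and SAP 5.1 repeats it. SAP 5.2 and Protocol 8.1.2 list eleven secondary endpoints; Protocol 10.2 lists twelve, adding ICU admission. Protocol 8.1.2 singles out day-30 symptom resolution ("The key secondary objective is"), but neither document attaches a testing role to that label. SAP Table 2 has a p-value column, and no p-value is marked as nominal.

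The success rule in the protocol is: "Non-inferiority will be concluded if the upper limit of the 95% confidence interval does not exceed the prespecified non-inferiority margin of 5" (per cent). SAP 10.1 decides instead on the confidence interval of an odds ratio. Neither rule mentions antibiotic use.

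The per-protocol set is primary for every efficacy variable (Protocol 10, SAP 8.2.3), and SAP 10.2.2 lists cumulative antibiotic consumption among these. Table 2 is a per-protocol table (SAP 9 and 17). Under SAP 9.3, a low-PCT patient who is nevertheless prescribed antibiotics is a major deviation and leaves that set.

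**The concern.** Two things are at stake, and neither is the primary claim.

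First, three benefits are worded as things to be established, but the plan does not say which tests carry that claim or in what order. A reader of the final report could not tell a confirmatory finding from one of eleven or twelve unadjusted p-values.

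Second, lower antibiotic use is the reason for accepting non-inferiority on treatment failure. The population chosen as primary for measuring it is selected on antibiotic use itself. A PCT-arm patient treated against the algorithm disappears; the usual-care arm has no comparable exclusion, because physicians there do not see the PCT result. The headline table can therefore show a reduction that the strategy did not achieve. Non-inferiority read beside that table could then be taken as evidence about withholding antibiotics when little was withheld.

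**Working it through.** **1. The plan's own sample size.** Inputs from SAP 7: failure 20.4% (usual care) and 16.7% (PCT arm), margin 5 points, one-sided 0.025, power 80%.

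n = (1.960 + 0.842)² × (0.204×0.796 + 0.167×0.833) / (0.05 + 0.037)² = 7.85 × 0.3015 / 0.00757 ≈ 313 per arm, as stated. At one-sided 0.0246 (half of the final 0.0492 in SAP 8.5.5) the same formula gives 315, also as stated. So nothing below questions the size of the primary comparison.

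**2. Error rate of the secondary objectives.** No level is stated. I infer two-sided 5% from the 95% intervals and the absence of any adjustment. With independent tests and all nulls true:

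- three stated objectives: 1 − 0.95³ = 14.3%
- eleven endpoints: 1 − 0.95¹¹ = 43.1%; twelve: 46.0%
- three objectives, counting only results in the favourable direction: 1 − 0.975³ = 7.3%

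SAP 10.2.2 treats a CAT difference below 2 points as clinically non-significant, so CAT contributes less than its full share. If that rule removed CAT altogether, the figure would be 1 − 0.95² = 9.8%. Positive correlation would typically lower all of these. The three-objective figure is the relevant one, because only those benefits are worded as claims.

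**3. Antibiotic use in the per-protocol set.** Let h be the share of patients with PCT above 0.25 µg/L, all treated, and o the share of the PCT arm with low PCT but given antibiotics. I read the SAP 9.3 exclusion as applying to the PCT arm, since PCT is withheld from usual care (Protocol 3).

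- true use in the PCT arm = h + o
- per-protocol use = h / (1 − o)

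Take the case of no true difference: both arms at 65%, the national figure in Protocol 1. Then o = 0.65 − h, and per-protocol use is h / (h + 0.35). The documents do not give h, so I assume 10–40%:

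| h | true use, each arm | per-protocol use, PCT arm | apparent fall |
|---|---|---|---|
| 10% | 65% | 0.10/0.45 = 22% | 43 points |
| 20% | 65% | 0.20/0.55 = 36% | 29 points |
| 30% | 65% | 0.30/0.65 = 46% | 19 points |
| 40% | 65% | 0.40/0.75 = 53% | 12 points |

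The mildest row would still usually test as significant. On a yes/no outcome starting from 315 per arm, 75% of the PCT arm (236) remain, the standard error is √(0.533×0.467/236 + 0.65×0.35/315) = 0.042, and z = 0.117/0.042 ≈ 2.8.

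This is the extreme case, since overruling has to be frequent (o = 25–55%) to cancel the true difference. With less overruling the bias is smaller: at h = 25% and o = 10%, true use is 35% and per-protocol use is 0.25/0.90 = 27.8%, an overstatement of about 7 points.

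**4. Non-inferiority when failure rates are equal.** Under the protocol's risk-difference rule, 315 per arm and 20.4% failure in both arms:

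Φ(0.05 / √(2×0.204×0.796/315) − 1.967) = Φ(−0.41) = 34%; at 16.7% in both arms it is 39%.

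**5. Power of an antibiotic-superiority test.** Yes/no use, 65% under usual care, 315 per arm, two-sided 5%: 25% if PCT-arm use is 60%, 73% at 55%, 97% at 50%. PCT-arm use is not given in the documents, and the planned variable is days rather than yes/no.

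**The case against.** The other side has a good deal right. There is one primary endpoint, and the two looks are handled separately in SAP 8.5.5, so unadjusted secondary tests cannot inflate the non-inferiority error. Leaving secondary endpoints unadjusted is common. Antibiotic use is a named objective, recorded at each visit and tested, and an ITT analysis is planned beside the per-protocol one. All of this stands. It does not remove the wording that sets out to establish three benefits, or the choice of the per-protocol set as primary for antibiotic use.

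Three stronger readings are tempting and go too far.

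- **That the trial can succeed vacuously, one time in three, with no separation between arms.** The 34% is power at equal failure rates, not an error rate: if the rates are equal, concluding non-inferiority is correct. Nor can overruling low PCT results erase separation in the deciding analysis, because those patients are excluded from it. Separation could vanish there only if usual-care prescribing fell to roughly the high-PCT share, and the documents' one figure for background use is 65%.
- **That any of the three benefits can be claimed on a chance p below 0.05.** The 2-point rule guards the CAT claim, and the 43% needs eleven independent endpoints, all null, although several measure the same symptom recovery.
- **That the trigger named in SAP 8.6 has been met.** SAP 4.2 still defines treatment failure as incomplete symptom resolution while SAP 5.2 uses the composite, so a change can be inferred. Nothing dates SAP 8.6 relative to it, and replacing one single primary by another creates no multiplicity.

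**Conclusion.** The point holds, limited to the secondary claims. The non-inferiority test and its sample size are not affected.

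The unordered objectives carry a false-positive chance of up to about 14% in either direction, or about 7% in the favourable direction. This rests on an inferred 5% level, independence and true nulls, and it is lower once the CAT rule is counted.

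The population problem weighs more. When there is no true difference in antibiotic use, the per-protocol comparison would show an apparent fall of 12 to 43 points for h between 40% and 10%. The size depends on h and on how often physicians overrule a low PCT, and the documents give neither. The direction follows from the exclusion rule itself.

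A reader might infer that antibiotic superiority should become a condition of trial success. The documents do not require it, and it is a genuine trade-off: with 80% power on the primary and 73% on antibiotic use, joint power is 0.80 × 0.73 = 58% if the two are independent.

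**What to change.** - **Population.** Make all randomised patients the primary population for cumulative antibiotic consumption, with per-protocol as supportive. Say all randomised explicitly: the ITT set in Protocol 10 and SAP 8.2.1 requires at least one dose of study drug, and if that were read as the antibiotic it would drop untreated patients.
- **Order.** Replace SAP 8.6 with a fixed sequence at the final-analysis level, after the primary: antibiotic consumption first, then the other two stated objectives in an order that the sponsor fixes now. Each step needs one named test, including one time point for CAT. Label all other secondary p-values nominal, including that for the key secondary, and say that its label carries no formal testing role.
- **Reporting.** Present the non-inferiority result beside the all-randomised difference in antibiotic use, so that a result with no separation is not read as evidence that withholding antibiotics is safe. Do not make antibiotic superiority a formal condition of trial success.

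The cost is wording: SAP 8.2.3, 8.6, 9 and 17, and a matching sentence in Protocol 10, which now makes per-protocol primary for all efficacy variables. Sample size does not change. The small downside is that later objectives lose formal status if an earlier step fails.

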9.1 Subject Disposition

For randomization, clinical data collection and central data management, Castor® will be used. Castor® is a web-based software tool designed to capture clinical study data. Castor® is hosted by an external party (Castor EDC), which is validated for conducting clinical trials in the Erasmus MC and meets all requirements to be ICH-GCP compliant.

One of Castor®'s prime features is that it keeps an audit trail, i.e. provides documentary evidence of the sequence of activities by user that have affected at any time a specific operation, procedure, or event. Data entry will be done according to Standard Operating Procedures. Besides, study specific data entry guidelines will be provided to local datamanagers, promoting a uniform and standardized way of data entry and providing ways of working in case of exceptions (i.e. missings, unknowns etc). The local datamanagers will be trained in using the eCRF system Castor® prior to data entry start. All trainings will be documented conform GCP requirements.

If data are complete for day 10 and day 30 then we consider this as a completion of the study for this study subject. If data from day 10 and or day 30 are missing every attempt will be made to collect the primary endpoint. When these attempts fail to collect the primary endpoint, this will be scored as a loss-to-follow-up.

An overview of the time-dependent rates of recruitment is provided below. This is of course a prediction and in agreement with ZonMW, who provided the required budget for this trial, we made

a prediction for 4 years. We aim to include all 690 in these four years, and according to our estimations this should be realistic:

Year 1

Month	Center 1	Center 2	Center 3	Center 4	Center 5	Center 6	Center 7	Center 8	Total cumul.
	SFG	EMC	RUMC	OLVG	AZ	NWZ	Isala	GH	
Mar-21	4	1	1	3	4	4	4	3	24
Apr-21	5	1	1	4	5	5	5	3	53
May-21	5	1	1	4	5	5	5	3	82
Jun-21	4	1	1	3	4	4	4	2	105
Jul-21	4	1	1	3	4	4	4	2	141
Aug-21	2	1	1	2	2	2	2	2	155
Sep-21	2	1	1	2	2	2	2	1	168
Oct-21	1	0	0	1	1	1	1	1	174
Nov-21	1	0	0	2	1	1	1	1	181
Dec-21	2	1	1	2	2	2	2	2	195
Jan-22	4	1	1	3	4	4	4	2	218
Feb-22	4	1	1	3	4	4	4	2	241
Total/year	38	10	10	32	38	38	38	24	

Year 2

Month	Center 1	Center 2	Center 3	Center 4	Center 5	Center 6	Center 7	Center 8	Total cumul.
	SFG	EMC	RUMC	OLVG	AZ	NWZ	Isala	GH	
Mar-22	4	1	1	3	4	4	4	3	265
Apr-22	5	1	1	4	5	5	5	3	294
May-22	5	1	1	4	5	5	5	3	323
Jun-22	4	1	1	3	4	4	4	2	346
Jul-22	4	1	1	3	4	4	4	2	369
Aug-22	2	1	1	2	2	2	2	2	383
Sep-22	2	1	1	2	2	2	2	1	396
Oct-22	1	0	0	1	1	1	1	1	402
Nov-22	1	0	0	2	1	1	1	1	409
Dec-22	2	1	1	2	2	2	2	2	423
Jan-23	4	1	1	3	4	4	4	2	446
Feb-23	4	1	1	3	4	4	4	2	469
Total/year	38	10	10	32	38	38	38	24	

Year 3

Month	Center 1	Center 2	Center 3	Center 4	Center 5	Center 6	Center 7	Center 8	Total cumul.
	SFG	EMC	RUMC	OLVG	AZ	NWZ	Isala	GH	
dec-22	4	1	1	3	4	4	4	3	493
jan-23	5	1	1	4	5	5	5	3	522
feb-23	5	1	1	4	5	5	5	3	551
mrt-23	4	1	1	3	4	4	4	2	574
apr-23	4	1	1	3	4	4	4	2	597
mei-23	2	1	1	2	2	2	2	2	611
jun-23	2	1	1	2	2	2	2	1	624
jul-23	1	0	0	1	1	1	1	1	630
aug-23	1	0	0	2	1	1	1	1	637
sep-23	2	1	1	2	2	2	2	2	651
okt-23	4	1	1	3	4	4	4	2	674
nov-23	4	1	1	3	4	4	4	2	697
Total/year	38	10	10	32	38	38	38	24	

Year 4

Month	Center 1	Center 2	Center 3	Center 4	Center 5	Center 6	Center 7	Center 8	Total cumul.
	SFG	EMC	RUMC	OLVG	AZ	NWZ	Isala	GH	
dec-23	4	1	1	3	4	4	4	3	721
jan-24	5	1	1	4	5	5	5	3	750
feb-24	5	1	1	4	5	5	5	3	779
mrt-24	4	1	1	3	4	4	4	2	802
apr-24	4	1	1	3	4	4	4	2	825
mei-24	2	1	1	2	2	2	2	2	839
jun-24	2	1	1	2	2	2	2	1	852
jul-24	1	0	0	1	1	1	1	1	858
aug-24	1	0	0	2	1	1	1	1	865
sep-24	2	1	1	2	2	2	2	2	879
okt-24	4	1	1	3	4	4	4	2	902
nov-24	4	1	1	3	4	4	4	2	925
Total/year	38	10	10	32	38	38	38	24	

CONSORT 2010 Flow Diagram

[figure not shown]

Figure 1. Consort flow diagram

9.2 Derived variables

The primary endpoint consists of several variables: disease-related mortality, endotracheal intubation, vasopressors, renal failure, lung abscess/empyema, pneumonia development and hospital readmission.

The key secondary endpoint is derived from the scores of the diary card with the modified Anthonisen criteria* the patient will fill in on baseline, day 3, day 5, day 10 and day 30. This endpoint will be scored by an independent physician. If there is incomplete resolution of symptoms, this will result in treatment failure. The symptoms are scored as categorical variables and include shortness of breath (slightly or much worse or 'as baseline condition prior to exacerbation'), sputum production (slightly or much more or 'as baseline condition prior to exacerbation'), sputum discoloration (slightly or strongly increased or 'as baseline condition prior to exacerbation') and minor symptoms as coughing, sore throat, fever, wheezing or a blocked or running nose. When one of these symptoms has not been resolved on day 30 this should result in scoring this as treatment failure.

*Example of the diary card with the modified Anthonisen criteria we used to derive our own diary card in Dutch. This original diary card was designed by Jaap Trappenburg et al. and used in a trial that was published in 2011 [15](Thorax 2011;66:977e984):

After evening diner

Compared with previous weeks ...	DAY 1 _/_/2009	DAY 1 _/_/2009	DAY 1 _/_/2009
I am more short of breath than normal	 No  Yes, slightly increased  Yes, clearly increased	 No  Yes, slightly increased  Yes, clearly increased	 No  Yes, slightly increased  Yes, clearly increased
I produce more sputum than normal	 No  Yes, slightly increased  Yes, clearly increased	 No  Yes, slightly increased  Yes, clearly increased	 No  Yes, slightly increased  Yes, clearly increased
My sputum is more green / yellow / brown than normal	 No  Yes, slightly increased  Yes, clearly increased	 No  Yes, slightly increased  Yes, clearly increased	 No  Yes, slightly increased  Yes, clearly increased
I have more complaints of:	 Coughing  Sore throat  Wheezing  Running nose / blocked nose  Fever (more than 38° C)	 Coughing  Sore throat  Wheezing  Running nose / blocked nose  Fever (more than 38° C)	 Coughing  Sore throat  Wheezing  Running nose / blocked nose  Fever (more than 38° C)

Figure 2. Anthonisen diary card

